4.2 Rationale for Study Design and Control Groups

The minimum age of 22 years in the inclusion criteria was selected based on:

- The legal age of smoking in the location of the chosen sites is 19 years.
- To account for the 3 years of smoking history.

This clinical study aims to demonstrate reductions in exposure to selected HPHCs in apparently healthy smokers switching to the THS 2.2 Menthol, a candidate MRTP, as compared to using mCCs (see IB Edition 2). The main reference in this study will be smokers who continue to smoke mCC. Smokers who stop smoking (the SA arm) will be used as a reference point for the maximum possible reduction in exposure to HPHCs.

The confinement period will provide information on maximum possible exposure reductions in a well-controlled environment and will allow full control of daily cigarette consumption. The ambulatory period will provide a perspective of product usage in the real world setting, where smoking of a few CC (menthol and non-menthol) in addition to THS 2.2 Menthol and SA is expected. It will provide information on reduction in selected BoExp and related changes in selected risk markers when THS 2.2 Menthol is used in a real world setting.

The choice of HPHCs to be assessed in this study is derived from the World Health Organization (WHO) (Ashley et al., 2008) and the draft guidance on Reporting Harmful and Potentially Harmful Constituents in Tobacco Products and Tobacco Smoke (FDA, 2011).

In the WHO list, 9 HPHCs (acrolein, CO, 1-3 butadiene, benzene, NNN, NNK, acetaldehyde, benzo[a]pyrene, and formaldehyde) with evidence of carcinogenicity, respiratory and cardiac

Data and information contained in this document are considered to constitute trade secrets and confidential commercial information, and the legal protections provided to such trade secrets and confidential information are hereby claimed under the provisions of United States law. No part of this document may be publicly disclosed without the written consent of Philip Morris International.

toxicity were recommended to be measured as priority in the smoke chemistry for mandated lowering (Ashley et al., 2008).

Exposure to 4 HPHCs (acrolein, CO, 1,3-butadiene, and benzene) among these 9 priority HPHCs will be assessed by measuring their respective BoExp as primary endpoints after 5 days of exclusive use of THS 2.2 Menthol, mCC or SA. The following characteristics apply to these primary BoExp:

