### 12.6.2 Secondary Analyses

The analysis of COHb, MHBMA, 3-HPMA, and S-PMA at Day 90 and Total NNAL at Day 5 will be repeated for the PP Set.

The analysis of the COHb, MHBMA, 3-HPMA, S-PMA at Day 5/ Day 90 and Total NNAL at Day 90 will be repeated for the FAS as described in Section 12.6.1.1 "Analysis of Biomarkers of Exposure for Primary Endpoints". These endpoints will also be examined to compare the reductions in THS 2.2 Menthol vs. SA using the same methodology as for the primary analysis for the PP Set.

The baseline is for the biomarkers measured in urine is as defined in Section 12.1.4 "Definitions for Statistical Data Analysis".

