#### 12.6.2.1 Analysis of Biomarkers of Exposure for Secondary Endpoints

The BoExp for the secondary endpoints are exhaled CO and total 1-OHP, Total NNN, 4-ABP, 1-NA, 2-NA, o-tol, CEMA, HEMA, B[a]P, HMPMA, S-BMA, Total NNAL and NEQ (all analysed from a 24-hour urine collection) at Day 5 and Day 90 will be described as reported in Section 12.1.3 "Descriptive Statistics". Urine parameters will be analyzed as concentrations adjusted for creatinine and the quantity excreted in urine over 24 hours. In addition the quantity excreted in urine over 24 hours for MHBMA, 3-HPMA, S-PMA and Total NNAL will also be presented as above.

All BoExp apart from CO breath test will be analyzed in the log scale.

BoExp will be analyzed using the same model described in Section 12.6.1.1 "Analysis of Biomarkers of Exposure for Primary Endpoints". No adjustment will be made for multiple comparisons. For all BoExp, if the results from the Day 5 analysis are significant (one-sided p-value  $\leq 0.025$ ) then the statistical significance will be evaluated for the results of the analysis at Day 90 values. LS means for each product along with the ratio (THS 2.2 Menthol : mCC) and 95% CI will be presented in the tables. Forest plots of the ratios and 95% CI will also be produced.

BoExp will also be examined to compare the reductions in THS 2.2 Menthol vs. SA using the same methodology as above for the PP Set. In addition, the sensitivity analyses described in Section 12.6.1.3 "Sensitivity Analysis" for the biomarkers of exposure for primary objectives will be repeated for the biomarkers of exposure for secondary objectives.

The data will be presented in the below outputs:

TFL number	Title
FIGURES	
15.1.1.2	Biomarkers of Exposure Geometric Mean and 95% CI – PP Set
15.1.1.4	Biomarkers of Exposure Geometric Mean and 95% CI – FAS
TABLES	
15.2.3.2	Analysis of COHb, MHBMA, 3-HPMA, S-PMA, and Total NNAL on Day 5/90 Visit versus mCC and SA for the Secondary Objective – PP Set.
15.2.3.3	Analysis of COHb, MHBMA, 3-HPMA, S-PMA, and Total NNAL on Day 5/90 Visit versus mCC and SA for the Secondary Objective – FAS.
15.2.3.4	Analysis of Additional Biomarkers of Exposure versus mCC and SA on Day 5/90 Visit – PP Set.
15.2.3.5	Analysis of Additional Biomarkers of Exposure versus mCC and SA on Day 5/90 Visit – FAS.
15.2.3.6	Sensitivity Analysis of Additional Biomarkers of Exposure versus mCC and SA using Mixed Model on Day 5/90 Visit – PP Set

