#### 12.6.2.4 CYP1A2 Activity

CYP1A2 activity will be measured in plasma on Day 0, Day 5 and Day 90. In this study the CYP1A2 activity will be calculated using the molar ratio of PX and CAF, as described in Section 7.1.3 “CYP1A2”. Descriptive statistics of the values and percent change on Days 5 and 90 from Day 0 and supportive listings will be provided.

The analysis will compare the log-transformed Day 5 values between the THS 2.2 Menthol and mCC arms and between the THS 2.2 Menthol and SA arms. ANCOVA models will be used on CYP1A2 activity levels with terms for log-transformed baseline, sex, average daily mCC consumption over the last 4 weeks as reported during screening and randomization arm. No adjustment will be made for multiple comparisons. If the results from the Day 5 analysis are significant (one-sided p-value <0.025) then the statistical significance will be repeated for the analysis at the Day 90 values. The SAS code will be similar to that described in Section 12.6.1.3 “Sensitivity Analysis”.

Geometric LS means for each product along with the ratio (THS 2.2 Menthol :mCC) and 95% CI will be presented in the tables.

CYP1A2 activity will also be examined to compare the observed reductions in THS 2.2 Menthol vs. SA using the same methodology as above.

If there are any CYP1A2 assessments performed within 5 half-lives since the use of a concomitant medication affecting CYP1A2 activity, the analysis will be repeated by excluding these assessments for both the PP Set and FAS

All summaries and analyses will be performed on the FAS and PP Set.

The data will be presented in the below outputs:

TFL number	Title
TABLES	
15.2.4.23.1	Descriptive Statistics of CYP1A2 Activity (%) – PP Set
15.2.4.23.1.1	Descriptive Statistics of CYP1A2 Activity (%) Excluding Assessments within 5 Half-Lives of a Concomitant Medication Affecting CYP1A2 Activity – PP Set
15.2.4.23.2	Descriptive Statistics of CYP1A2 Activity (%) – FAS
15.2.4.23.2.1	Descriptive Statistics of CYP1A2 Activity (%) Excluding Assessments within 5 Half-Lives of a Concomitant Medication Affecting CYP1A2 Activity – FAS
15.2.4.24.1	Analysis of CYP1A2 Activity (%) – PP Set
15.2.4.24.1.1	Analysis of CYP1A2 Activity (%) Excluding Assessments within 5 Half-Lives of a Concomitant Medication Affecting CYP1A2 Activity – PP Set
15.2.4.24.2	Analysis of CYP1A2 Activity (%) – FAS

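### THS vs SA inherits a one-sided test, and in places an early significance gate, from THS vs mCC with no direction stated for SA; read as THS lower, the p-value is uninformative at the plan's own expected ratios

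*SAP*

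**What the plan says.** Four SAP sections set the THS vs SA analysis by reference to the THS vs mCC analysis.

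- **SAP 12.6.2 (primary biomarkers).** "These endpoints will also be examined to compare the reductions in THS 2.2 Menthol vs. SA using the same methodology as for the primary analysis", on the PP Set. The primary analysis in SAP 12.6.1.1 is an ANCOVA on the log scale, reporting the ratio, a two-sided 95% CI and a one-sided p-value. It contains no Day 5 to Day 90 gate.
- **SAP 12.6.2.1 (secondary biomarkers).** The gate reads "For all BoExp, if the results from the Day 5 analysis are significant (one-sided p-value" at most 0.025), "then the statistical significance will be evaluated for the results of the analysis at Day 90 values". The SA sentence follows in the next paragraph: "BoExp will also be examined to compare the reductions in THS 2.2 Menthol vs. SA using the same methodology as above", on the PP Set. The ratio named for presentation is THS:mCC only.
- **SAP 12.6.2.4 (CYP1A2).** Both contrasts, THS vs mCC and THS vs SA, are named before a one-sided 0.025 gate from Day 5 to Day 90. Then: "CYP1A2 activity will also be examined to compare the observed reductions in THS 2.2 Menthol vs. SA using the same methodology as above".
- **SAP 12.6.3.4 (CYP2A6).** The same pattern, with the gate running from Day 6 to Day 91.

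The only direction written for a biomarker of exposure is in SAP 5.5.1 and 12.6.1.2: THS lower, relative to mCC. Protocol 4.2 gives the role of the abstinence arm: "Smokers who stop smoking (the SA arm) will be used as a reference point for the maximum possible reduction in exposure to HPHCs". Protocol 12.1.5 makes tests two-sided at 5% unless stated otherwise.

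**The concern.** A test that THS lies below the comparator is right for mCC and wrong for abstinence. If SA marks the largest reduction available, the useful question is how far THS stays above it. A one-sided p-value for THS below SA would be near 1 when exposure is double that of abstinence. It would also be non-significant when the two are equal, apart from type I error. It therefore cannot separate these cases, and a large p-value beside a THS:SA ratio invites the reading that THS is no different from quitting.

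Where the gate applies, failing it at the early time point also means that significance against SA at Day 90 is not evaluated. Nicotine equivalents illustrate the misfit. They fall under SAP 12.6.2.1, yet Protocol 2.1.2 says the product is meant to deliver nicotine much as cigarettes do, so an alternative of THS below abstinence is hard to motivate.

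**Working it through.** **Inputs.** SAP Table 16 gives expected Day 5 THS:SA mean ratios (CV): COHb 2.10 (0.20), 3-HPMA 1.70 (0.33), MHBMA 1.00 (0.35), S-PMA 1.15 (0.42). SAP Table 1 gives 80 THS and 40 SA subjects.

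**Formulas.** SD on the log scale = sqrt(ln(1 + CV²)). SE = SD × sqrt(1/n1 + 1/n2), with sqrt(1/80 + 1/40) = 0.1936.

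**Check on the plan's own figures.** For a 50% reduction against mCC, power per marker is Φ(ln(0.5/MR)/SE − 1.96), multiplied over the five markers (80:40, and 40:40 for Total NNAL).

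- YVD-CS01-EU assumptions: COHb has SD 0.312, SE 0.0605 and power 0.958. Total NNAL has SD 0.555, SE 0.124 and power 0.985. The others are close to 1. The product is 94.3%; SAP Table 20 states 94%.
- ZRHX-EX-01 assumptions: 98.2%; SAP Table 20 states 98%.
- Protocol 12.2 plans THS:SA confidence limits within 18% of the estimate with 80% overall probability. At 80:40 the joint probability over the four markers is 0.87, so this is met.

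Other columns of Table 20 match only in part (ZRHX-EX-01 at 53%: 65% computed, 76% stated). This does not bear on the point.

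**THS vs SA.** The chance of significance for THS lower is Φ(−z − 1.96), where z = ln(MR)/SE. The two-sided 5% power is, to the accuracy shown, Φ(z − 1.96) + Φ(−z − 1.96).

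| Marker | SD | SE | ln(MR) | z | One-sided, THS lower | Two-sided 5% |
|---|---|---|---|---|---|---|
| COHb | 0.198 | 0.0383 | 0.742 | 19.35 | about 0 | about 100% |
| 3-HPMA | 0.322 | 0.0623 | 0.531 | 8.52 | about 0 | about 100% |
| S-PMA | 0.403 | 0.0781 | 0.140 | 1.79 | 0.01% | 43% |
| MHBMA | 0.340 | 0.0658 | 0 | 0 | 2.5% | 5% |

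The MHBMA entries are type I error, because its expected ratio is 1.00. For 80% power in the THS-lower direction the true THS:SA ratio would have to be exp(−2.80 × SE): 0.90 for COHb, 0.84 for 3-HPMA, 0.83 for MHBMA and 0.80 for S-PMA. All lie below what the plan expects.

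**What the intervals already show.** At 80:40 the upper limit of the 95% CI is 7.9% above the estimate for COHb, 13.1% for 3-HPMA, 13.9% for MHBMA and 16.7% for S-PMA. At the expected COHb ratio the interval is about 2.10/1.079 to 2.10 × 1.079, or 1.95 to 2.27. With 40:40 at Day 90, assuming that the Day 5 CVs carry over and no SA subject leaves the PP Set, the upper limits run from 9.2% to 19.7% above the estimate.

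**Where the gate sits.** The four markers in the table are primary biomarkers, and SAP 12.6.2 sends their SA comparison to the ungated primary analysis. The gate is in SAP 12.6.2.1, 12.6.2.4 and 12.6.3.4, and the documents give no THS:SA ratio for the secondary markers, CYP1A2 or CYP2A6. The table therefore describes the one-sided p-value for four primary markers. It is not a gate-opening probability for the gated ones.

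**The case against.** The strongest reply is that the SAP nowhere writes a test of THS below SA. Every stated direction is against mCC, and Protocol 12.6.4 defines its own Day 5 then Day 90 rule through the THS vs mCC hypothesis. With no direction given for SA, the two-sided default of Protocol 12.1.5 could govern, and the same methodology could mean just the ANCOVA with its ratio and interval. The same one-sided rule for CYP2A6, where Protocol 4.2 asks only whether the product affects the enzyme, suggests that one-sided 0.025 may be shorthand for the 5% level. Under a two-sided test, or one in the THS-higher direction, COHb and 3-HPMA would be significant almost surely and S-PMA about 43% of the time.

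This stands as a limit on certainty: the direction is imported, not written. It does not remove the problem. SAP 12.6.2 imports an analysis whose stated output is a one-sided p-value, and SAP 12.6.2.4 names the SA contrast before its one-sided gate, so the default is at least arguably displaced.

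A reader might also infer that THS vs SA significance at Day 90 is practically never evaluated, with the gate opening in at most 2.5% of trials per marker. The documents do not support that. The markers with THS:SA ratios have no explicit gate. The phrase covering all biomarkers in SAP 12.6.2.1 could be read to reach them, but the section concerns secondary endpoints and does not list COHb.

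Finally, estimation survives. Protocol 3.2 sets the SA objective for biomarkers as describing levels, Protocol 12.2 plans THS:SA interval precision, and SAP Tables 15.2.3.2 to 15.2.3.7 are titled to cover mCC and SA on Day 5/90. A two-sided 95% CI that excludes 1 does the work of a two-sided 5% test. This stands in full and limits the harm.

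**Conclusion.** The point holds as a defect of specification. The SAP applies a one-sided analysis to THS vs SA, with an early gate in three sections, without stating a hypothesis or direction for that contrast. On the only direction it does state, the p-value could be significant at most 2.5% of the time at the expected ratios for the four primary markers. A two-sided test would detect the COHb and 3-HPMA differences almost surely.

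The figures rest on the Table 16 Day 5 ratios and CVs, log-normal data, 80:40 subjects and the THS-lower reading. No probability can be given for the gated secondary markers, CYP1A2 or CYP2A6.

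The harm is uninformative, easily misread p-values and Day 90 significance against SA that may be withheld. The SA estimates and intervals are not lost, and the primary THS vs mCC conclusion does not depend on any of this. It should be corrected because the rule does not fit the comparison and the correction is nearly free.

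**What to change.** In SAP 12.6.2, 12.6.2.1, 12.6.2.4 and 12.6.3.4, state that:

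- THS vs SA is reported as the THS:SA geometric mean ratio with a two-sided 95% CI at both the early time point (Day 5, or Day 6 for CYP2A6) and the Day 90 Visit. For exhaled CO, which is analysed untransformed, report the difference.
- Any THS vs SA p-value is two-sided at the 5% level.
- The early-time-point gate applies only to THS vs mCC.

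This changes SAP wording and table specifications only. It needs no new data, sample size or model. The cost is a few more unadjusted p-values among secondary and exploratory comparisons, which the SAP already leaves unadjusted.

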### 12.6.2.2 Nicotine and Cotinine Concentrations

The concentrations of nicotine and cotinine will be listed and summarized. During confinement, the evening concentration levels at 08:00 PM is considered. Baseline is the assessment at 08:00 PM to 09:30 PM on Day 0. Line graphs of the nicotine and cotinine concentration profiles across all study days showing mean and 95% CI will also be produced.

Nicotine and cotinine concentrations at each post-baseline timepoint separately will be analysed in the log space using an ANCOVA model with terms for log-transformed baseline concentration, sex, average daily mCC consumption over the last 4 weeks as reported during screening, and product. No adjustment will be made for multiple comparisons.

The SAS code described in Section 12.6.1.3 “Sensitivity Analysis” will be used for the analysis of nicotine and cotinine.

Geometric LS means for each product along with the ratio (THS 2.2 Menthol : mCC) and 95% CI will be presented in the tables.

All figures, summaries and analyses will be performed on the PP Set and FAS by randomization arm.

The data will be presented in the below outputs:

TFL number	Title
FIGURES	
15.1.2.1.1	Plasma Nicotine and Cotinine Profile (ng/mL) over the 90 Days Geometric Mean and 95% CI – PP Set
15.1.2.1.2	Plasma Nicotine and Cotinine Profile (ng/mL) over the 90 Days Geometric Mean and 95% CI – FAS
TABLES	
15.2.4.19.1	Descriptive Statistics of Plasma Nicotine and Cotinine Concentrations (ng/mL) – PP Set
15.2.4.19.2	Descriptive Statistics of Plasma Nicotine and Cotinine Concentrations (ng/mL) – FAS
15.2.4.20.1	Analysis of Plasma Nicotine and Cotinine Concentrations (ng/mL) over the 90 Days – PP Set
15.2.4.20.2	Analysis of Plasma Nicotine and Cotinine Concentrations (ng/mL) over the 90 Days – FAS
LISTINGS	
15.3.3.3	Listing of Plasma Nicotine and Cotinine Concentrations

### 12.6.2.3 Nicotine and Cotinine Pharmacokinetic Parameters

The parameters  $C_{peak}$ ,  $C_{avg}$  and  $t_{peak}$  will be calculated on Day 5 as described in Section 7.2 “**Pharmacokinetic Parameters**”. The data will be listed and summarized for both nicotine and cotinine.

The analysis will compare the log-transformed  $C_{peak}$  and  $C_{avg}$  on Day 5 between the THS 2.2 Menthol and mCC arms. An analysis of variance (ANOVA) model will be used with terms for sex, average daily mCC consumption over the last 4 weeks as reported during screening and randomization arm.

The SAS code will be similar to that described in Section 12.6.1.3 “**Sensitivity Analysis**”, with no baseline value being included in the model.

LS means for each product along with the ratio (THS 2.2 Menthol : mCC) and 95% CI will be presented in the tables.

For  $t_{peak}$  on Day 5 the comparison between the THS 2.2 Menthol and mCC arms will be made by the Wilcoxon Rank Sum test using PROC NPAR1WAY in SAS. Median difference and 95% CI using the Hodges-Lehmann estimate will be tabulated.

The following code will be used:

```
Proc npar1way data=_data_ hl median;
Class randomization_arm;
Var tpeak;
Run;
```

All summaries and analyses will be performed on the PP Set and FAS.

The data will be presented in the below outputs:

TFL number	Title
TABLES	
15.2.4.21.1	Descriptive Statistics of Plasma Nicotine and Cotinine PK Parameters on Day 5 – PP Set
15.2.4.21.2	Descriptive Statistics of Plasma Nicotine and Cotinine PK Parameters on Day 5 – FAS
15.2.4.22.1	Analysis of Plasma Nicotine and Cotinine PK Parameters on Day 5 – PP Set
15.2.4.22.2	Analysis of Plasma Nicotine and Cotinine PK Parameters on Day 5 – FAS
LISTINGS	
15.3.3.4	Listing of Plasma Nicotine and Cotinine Pharmacokinetic Parameters on Day 5

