7.5.1.2 Plasma Nicotine and Cotinine

Nicotine and cotinine concentrations will be measured in plasma to evaluate the exposure to nicotine in all three study arms. No sampling for PK profile will be done for subjects in the SA arm (Day 5 to Day 6) and only one blood sampling will be done on each of Day 5 and Day 6.

- On Day 0 to Day 4 (all study arms):

One blood sample per day will be taken in the evening between 08:00 PM and 09:30 PM.

- Nicotine/Cotinine Pharmacokinetic (PK) Profile on Day 5 and Day 6 (THS 2.2 Menthol and mCC arms only):

In total, 9 blood samples will be drawn on Day 5. The first blood sample on Day 5 will be drawn within 15 minutes prior to the first product use. On Day 5, the start time of the first product use (T_0) will serve as reference for the time to peak concentration. An additional 8 blood samples will be drawn in 2 hour intervals after the start of product use. The last blood sample should be drawn no later than 11:00 PM, corresponding to the end of product use. At all time points, if the subject wants to use the product around the time of

the blood draw, he/she should use it first and the blood will be drawn after product use. Depending on the time of the first product use, it may be that fewer than 8 blood samples will be collected from a subject after T_0 .

On Day 6, two blood samples will be drawn. The first one will be 20 hours after T_0 and the second blood sample will be 24 hours after T_0 (with T_0 being the start time of first product use at Day 5).

- On Day 5 and Day 6 (SA arm only):

On Day 5, one blood sample will be drawn in the evening between 08:00 PM and 09:30 PM.

On Day 6, one blood sample will be drawn between 08:00 AM-09:30 AM.

- On Day 30 Visit (Day 30), Day 60 Visit (Day 60), Day 90 Visit (Day 90) (all study arms):

One blood sample will be drawn during these visits, irrespective of the time of product use.

7.5.1.3 *Other Biomarkers of Exposure*

BoExp will be measured as per the Schedule of Events (Appendix 1):

- In 24-hour urine collection samples during both confinement and ambulatory periods from Day 0 onwards to Day 5 and on Day 30 Visit, on Day 60 Visit , and on Day 90 Visit.
- In 4-hour urine fraction during both confinement and ambulatory periods collected on Day -1, and Day 90 Visit (Day 91).

The following BoExp will be measured:

- Selected primary BoExp: MHBMA, 3-HPMA, S-PMA, and Total NNAL.

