  - Nicotine equivalents (NEQ) (expressed in quantity excreted and concentration adjusted for creatinine) in 24-hour urine from Day 1 to Day 5, Day 30 Visit, Day 60 Visit and Day 90 Visit.
  - Nicotine and cotinine in plasma from Day 1 to Day 4, Day 5, Day 30 Visit, Day 60 Visit, and Day 90 Visit.

5. To describe the pharmacokinetic (PK) profiles of nicotine and cotinine in smokers in a confinement setting switching from mCC to THS 2.2 Menthol as compared to smokers continuing to smoke mCC.

Endpoints:

- Peak (highest concentration value along the day) on Day 5.
- Time to peak (actual time when the peak was observed compared to the time of the first cigarette) on Day 5.
- Weighted average concentration over 24 hours on Day 5.

6. To describe the change in Cytochrome P450 1A2 (CYP1A2) enzymatic activity in smokers switching from mCC to THS 2.2 Menthol as compared to smokers continuing to smoke mCC and SA.

Endpoint:

- Molar metabolic ratio of paraxanthine (PX)/caffeine (CAF) in plasma on Day 5 and Day 90 Visit.

7. To determine the changes in lung function in smokers switching from mCC to THS 2.2 Menthol as compared to those continuing to smoke mCC.

Endpoint:

Full lung functions:

- Diffusion capacity for lung CO (DLCO).
- Rate constant for lung CO (KCO).
- Forced expiratory volume in 1 second (FEV1).
- Forced vital capacity (FVC).
- Vital capacity (VC) expressed as L.
- Total lung capacity (TLC).
- Forced residual volume (FRV).
- Inspiratory capacity (IC).
- Mid expiratory flow (25-75)

8. To monitor the safety profiles during the study.

Endpoints:

- AEs, SAEs and device events, including THS 2.2 Menthol malfunction and misuse.
- Respiratory symptoms: cough assessment by visual analogue scale (VAS), Likert scales, and one open question.
- Vital signs.
- Electrocardiogram (ECG).
- Clinical chemistry, hematology, and urine analysis safety panel.
- Physical examination.
- Concomitant medications.

9. To monitor selected risk markers in a confinement and ambulatory setting in smokers switching from mCC to THS 2.2 Menthol as compared to smokers continuing to smoke mCC and to SA.

Endpoints:

- Systolic and diastolic blood pressure on Day 6, Day 30 Visit, Day 60 Visit, and Day 90 Visit.
- High sensitive C-reactive protein (hs-CRP), homocysteine, blood glucose, low density lipoprotein (LDL), high density lipoprotein (HDL), triglycerides (TG), and total cholesterol (TC) in serum on Day 30 Visit, Day 60 Visit, and Day 90 Visit.

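### The Day 5 nicotine and cotinine Cpeak and Cavg models could probably gain precision, at almost no cost, by adjusting for the Day 0 evening concentration

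*SAP*

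**What the plan says.** SAP 12.6.2.3 fits an ANOVA to the log-transformed Day 5 Cpeak and Cavg with "terms for sex, average daily mCC consumption over the last 4 weeks as reported during screening and randomization arm". It adds that the code follows an earlier section but "with no baseline value being included in the model". The result is reported as a THS 2.2 Menthol to mCC ratio with a 95% CI. No reason is given for leaving baseline out.

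Protocol 7.5.1.2 plans nicotine and cotinine sampling from Day 0 to Day 4 in all study arms: "One blood sample per day will be taken in the evening between 08:00 PM and 09:30 PM". Subjects are told their arm on Day 1 before 06:30 AM (Protocol 4.1), so the Day 0 evening sample is drawn while everyone is still smoking their own mCC and does not yet know the allocation.

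SAP 12.6.2.2 treats that sample as the baseline for these analytes: "Baseline is the assessment at 08:00 PM to 09:30 PM on Day 0". It analyses single concentrations at each post-baseline timepoint with an "ANCOVA model with terms for log-transformed baseline concentration", plus sex, consumption and product.

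The serial profile that yields the two parameters is taken only on Day 5 to Day 6, in the THS 2.2 Menthol and mCC arms. Cpeak is the "Peak (highest concentration value along the day) on Day 5", and Cavg is AUC over 24 hours divided by 24 (SAP 7.2). The objective they serve is secondary and worded "To describe the pharmacokinetic (PK) profiles of nicotine and cotinine in smokers in a confinement setting".

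**The concern.** A baseline covariate need not be the same quantity as the outcome. It must be unaffected by the assigned product and should correlate with the outcome. The Day 0 evening concentration meets the first condition, and it is likely to meet the second because it is the same analyte in the same person a few days earlier. The SAP already relies on it one section before.

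The omission also stands apart from the rest of the SAP. The other model-based arm comparisons adjust for baseline: primary and secondary biomarkers, single nicotine and cotinine concentrations, CYP1A2, CYP2A6, risk markers, the 4-hour urine fraction, the smoking-urge, product-evaluation and withdrawal questionnaires, and topography.

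What is at stake is the width of the interval around the nicotine and cotinine exposure ratios, in a comparison with only 40 planned mCC subjects. No primary or powered result is involved.

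**Working it through.** **No plan figure to reproduce.** Neither document gives an SD, correlation, power or precision target for Cpeak or Cavg. The power tables (Protocol Table 23, SAP Table 20) concern the five primary biomarkers.

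**Inputs.** There are 80 THS 2.2 Menthol and 40 mCC subjects (SAP Section 8), so N = 120 in this two-arm comparison. The planned model has four parameters (intercept, sex, consumption, arm), leaving 120 − 4 = 116 error df. With one covariate, 120 − 5 = 115 remain. Let ρ be the partial correlation between the log Day 0 evening level and the log Day 5 parameter given sex, consumption and arm. The documents do not give ρ, so a range is assumed.

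**Formula.** Expected variance ratio, adjusted to unadjusted = (1 − ρ²) × (1 + 1/(115 − 1)) = (1 − ρ²) × 1.0088. The second factor is the average price of chance imbalance in the covariate. The CI width ratio on the log scale is the square root of the variance ratio; the change in the t quantile is negligible. The sample-size equivalent is the reciprocal of the variance ratio.

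| Assumed ρ | Variance ratio | CI width ratio | Sample-size equivalent |
|---|---|---|---|
| 0 | 1.009 | 1.004 | 0.99 |
| 0.1 | 0.999 | 0.999 | 1.00 |
| 0.3 | 0.918 | 0.958 | 1.09 |
| 0.5 | 0.757 | 0.870 | 1.32 |
| 0.7 | 0.514 | 0.717 | 1.94 |
| 0.8 | 0.363 | 0.603 | 2.75 |

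Break-even is where (1 − ρ²) × 115/114 = 1, so ρ = √(1/115) ≈ 0.09. Simulating 3,000 trials per value gave width ratios of 1.004, 0.958, 0.869 and 0.719 at ρ = 0, 0.3, 0.5 and 0.7, in agreement.

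**On the ratio scale.** Assume a residual CV of 0.50 and an estimated ratio of 1. The log SD is √ln(1 + 0.50²) = 0.472 and the SE is 0.472 × √(1/80 + 1/40) = 0.0915. With no gain from baseline the 95% CI is 0.834 to 1.199. Multiplying the SE by √(1 − ρ²) gives 0.841 to 1.189 at ρ = 0.3, 0.855 to 1.170 at 0.5, and 0.879 to 1.138 at 0.7.

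**Why partial correlation.** Sex and consumption are already in the model, so the simple within-arm correlation overstates the gain. As an illustration, assume these two terms explain 15% of both variables through a shared component. The partial value is then (r − 0.15)/0.85, so within-arm correlations of 0.3, 0.5, 0.7 and 0.8 become about 0.18, 0.41, 0.65 and 0.76. Using √(1 − ρ²), the SE falls by about 2%, 9%, 24% and 36%, rather than the 5%, 13%, 29% and 40% from the unreduced values.

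**The case against.** The case for leaving the model alone has several parts.

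- **No matching baseline exists.** There is no Day 0 serial profile and so no baseline Cpeak or Cavg. Where the SAP adjusts, it generally uses the baseline of the same variable. This explains the omission and makes it defensible, but it does not make the evening value unsuitable as a covariate.
- **Sampling conditions differ.** On Day 5 a subject who wants to use the product near a draw uses it first (Protocol 6.6.1.1 and 7.5.1.2); no such rule is stated for Day 0. On Day 0, compatible mCC are smoked through the topography device, which is not planned for Day 5 (Protocol 7.8.2). Two thirds of the comparison (80 of 120) is on a different product by Day 5. These are good reasons not to assume a high correlation, and that caution stands.
- **Baseline-adjusted nicotine exposure is analysed elsewhere.** Evening concentrations (SAP 12.6.2.2) and 24-hour urinary nicotine equivalents (SAP 12.6.2.1) are both adjusted. This lowers the importance of the point but does not sharpen the Cpeak and Cavg intervals.
- **Subjects could be lost.** SAP 12.1.5 does not impute missing baselines (stated under laboratory parameters), so a subject without a Day 0 value would leave the adjusted model. Keeping the unadjusted model as supportive answers this.

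A reader might infer that the comparison is biased, or that chance imbalance invalidates it. Randomisation is blocked within sex and consumption strata, both factors are in the model, and the CI already allows for chance imbalance. The estimate is unbiased and the type I error rate is unaffected.

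**Conclusion.** The point holds as a low-cost efficiency improvement. The Day 0 evening value is planned in all arms, is already accepted as baseline for the same analytes, and costs one error df: about 0.4% in CI width if it carries no information, with break-even at a partial correlation near 0.09. At assumed partial correlations of 0.3, 0.5 and 0.7 the CI narrows by about 4%, 13% and 28%. The existence of the omission is certain; the size of the gain is not.

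Two stronger readings are tempting. One is that precision is discarded for no reason at all. The lack of a like-for-like baseline profile is a plausible reason, although the SAP does not state it. The other is that the omission costs the equivalent of doubling or more of the sample. That needs a partial correlation above 0.7, for which the documents offer no support.

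No success criterion, power statement or multiplicity-controlled claim depends on this comparison.

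**What to change.** In SAP 12.6.2.3, add log(Day 0 evening nicotine) to the nicotine Cpeak and Cavg models and log(Day 0 evening cotinine) to the cotinine models, with baseline defined as in SAP 12.6.2.2. Keep the unadjusted ANOVA as a supportive analysis, so that a subject with a complete Day 5 profile but no Day 0 sample is still included there. Report the number of subjects in each.

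The cost is one term per model and one degree of freedom, with no new samples or visits. If the sponsor prefers to keep the current model as the main one, a sentence giving the reason would be enough, with the adjusted model shown as supportive.
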